### **8.6.3. Sensitivity Analyses of the Key Secondary Efficacy Results**

Robustness of the key secondary efficacy endpoints due to missing data or premature treatment discontinuations (including the impact of COVID-19) will be explored by the following sensitivity analyses:

- Tipping point approach of the MI analysis as described in [Section 6.6.1.2](#)
- Mixed model random coefficients analysis using observed data (with no imputation of missing data)
- Mixed model random coefficients analysis using completers only (patients who completed treatment through 1-year and 2-year blind treatment period)
- Mixed model random coefficients analysis including local laboratory data with central laboratory data
- Mixed model random coefficients using observed data (with no imputation of missing data) during the double-blind period including after premature treatment discontinuation (treatment policy estimand). Additional analysis exploring potential intercurrent events that could impact the primary analysis (eg, premature discontinuation of study drug, use of immunosuppressive agents, loss to follow-up, withdrawal of consent, need for RRT, or death) may be performed to examine their impact.

To assess the impact of changes in immunosuppressive medications, the key secondary efficacy analysis will be repeated by excluding assessments after initiation of renal indication of systemic immunosuppressive medication in the blinded treatment period.

To assess the potential impact of patient evaluability and major protocol deviations, the key secondary efficacy analysis will be repeated using the PP Analysis Set.

#### **8.6.3.1. Sensitivity Analysis of the eGFR Chronic Slopes**

Sensitivity analysis of the key secondary efficacy endpoints of the eGFR slopes over 52 weeks and 104 weeks, defined as the slopes of eGFR following the initial acute effect of randomized treatment (ie, Week 6 to Week 58 and to Week 110), will be analyzed via a mixed-effects model with linear spline (ie, a 2-slope model with knot or change point at Week 6) with available eGFR data at primary analysis for 1 year and at the final analysis for 2 years. The response variable is the eGFR measured at on-treatment, post-baseline assessments during the randomized treatment period up to and including Week 58 (and Week 110) for each patient. The model will include the following fixed effects:

- Treatment group (2 levels: sparsentan, irbesartan)
- Baseline eGFR
- Time from baseline (analysis visit, in weeks)
- Time from change point (in weeks)
- Treatment group by time from baseline interaction
- Treatment group by time from change point interaction
- Randomization stratification variable (4 levels based on Screening eGFR and urine protein excretion)

In addition, the model will also include a random intercept and random slopes (time from baseline and time from change point) for each patient. The mixed model will utilize restricted maximum likelihood estimation with Kenward-Roger method to compute the denominator degrees of freedom for tests of fixed effects. An unstructured covariance matrix will be assumed. If convergence issues arise, the autoregressive-1 covariance structure will be used.

The associated slope estimates within treatment group, difference in slopes, 95% CI, and 2-sided p-value will be extracted from the model. The treatment effect for the slope following the change point at Week 6 (ie, difference in slopes) will be the sum of the coefficients for the treatment group by time from baseline interaction and treatment group by time from change point interaction estimated from the model. Slope and the difference in slopes will be annualized for ease of presentation and interpretation.

### **8.7. Analysis of Other Secondary and Exploratory Endpoints**

All other secondary and exploratory endpoints will be evaluated using the FAS.

Use of systemic immunosuppressive medication for renal indication will be determined via medical review of concomitant medications and associated indications, and be done prior to each database lock and unblinding.

Kidney-related hospitalizations will be determined via medical review of serious AEs and be performed prior to each database lock and unblinding.

### **8.7.1. Rate of Change in eGFR over 58 Weeks Following Initiation of Randomized Therapy**

The rate of change in eGFR over 58 weeks following the initiation of randomized therapy will be analyzed via a mixed model random coefficients analysis using the PAS at the time of primary analysis and the FAS at final analysis.

The response variable is the eGFR measured at on-treatment, post-baseline assessments during the randomized treatment period up to and including Week 58 for each patient. The model will include the following fixed effects:

- Treatment group (2 levels: sparsentan, irbesartan)
- Baseline eGFR
- Time (ie, analysis visit in weeks)
- Treatment group by time interaction
- Randomization stratification variable (4 levels based on Screening eGFR and urine protein excretion)

In addition, random intercept and random slope will be included for each patient.

Under the assumption of MAR, missing data will be imputed using the MI procedure (Ouyang 2017, Rubin 1987). Specific imputation procedures are provided in [Section 6.6.1.1](#).

An unstructured covariance matrix will be assumed; if convergence issues arise, a first order autoregressive structure will be used.

The treatment effect will be the contrast between sparsentan and irbesartan marginal slope estimates. The associated slope estimates, difference in slopes, 95% CI, and 2-sided p-value will be extracted from the model. Slope and the difference in slopes will be annualized for ease of presentation and interpretation.

### **8.7.2. Change in eGFR from Baseline to 4 Weeks Post-cessation of Randomized Treatment (Week 114)**

The change from baseline to 4 weeks post-cessation of randomized treatment (114 weeks) will be analyzed via analysis of covariance (ANCOVA). The dependent variable will be the change from baseline eGFR at the analysis visit at Week 114. The model will include the following fixed effects:

- Treatment group (2 levels: sparsentan, irbesartan)
- Baseline eGFR
- Randomization stratification variable (4 levels based on Screening eGFR and urine protein excretion)

The treatment effect will be the contrast between sparsentan and irbesartan LS means. The LS means, treatment effect estimate (difference in LS means), 95% CI, and p-value will be presented.

Robustness of the analysis due to missing data and premature treatment discontinuations will be explored by assessing the change from baseline to 4-weeks post EOT analysis visit.

### **8.7.3. Other Continuous Endpoints**

The following exploratory endpoints will be analyzed using an MMRM as described for the primary efficacy endpoint ([Section 8.5.1](#)). Missing data will not be imputed using the MI procedure:

- The mean change from baseline in eGFR and selected proteinuria variables, based on a 24-hour urine sample (eg, urine protein excretion, urine albumin excretion, UA/C, and UP/C), up to Week 110
- Mean changes from baseline in QoL, measured via PRO at each visit
- Change from baseline for blood pressure will also be analyzed at both primary analysis and at final analysis.

The following exploratory endpoints will be analyzed using an ANCOVA analysis:

- The change from baseline in eGFR at 6 weeks post randomization (ie, the acute effect of randomized therapy)
- The change from EOT (ie, Week 110) in eGFR 4 weeks following cessation of treatment (ie, at Week 114)
- Duration of hospitalizations (for any reason and for reasons related to the kidney)

Specifically, the change from baseline or EOT or duration (as applicable) will be the dependent variable, treatment group, and randomization stratification strata as fixed effects and baseline value as covariate. The treatment effect will be the contrast between sparsentan and irbesartan LS means. The LS means, treatment effect estimate, 95% CI, and p-value will be presented.

### **8.7.4. Other Responder Endpoints**

Responder endpoints will be summarized at both the primary and final analysis. For these responder endpoints, patients are classified as either a responder or a non-responder.

The following endpoints will be analyzed via a logistic regression model with a fixed effect for treatment and baseline eGFR (baseline urinary protein excretion for complete remission defined as urinary protein excretion <0.3 g/day, partial remission defined as urinary protein excretion <1.0 g/day) as a covariate, stratified by the randomization strata:

- The proportion of patients reaching a confirmed 40% reduction in eGFR, ESRD, or death
- The proportion of patients achieving urinary protein excretion <0.3 g/day up to Week 110

- The proportion of patients achieving urinary protein excretion  $<1.0$  g/day up to Week 110

The treatment effect estimate from the model will be the contrast between sparsentan and irbesartan log odds. The treatment effect estimate and its 95% CI will be back-transformed to provide results on the odds ratio scale, and the associated 2-sided p-value will be presented.

Reduction of eGFR requires confirmation by a value at least 4 weeks after the initial value. If the last value on randomized treatment is the initial value for reduction or eGFR  $<15$  mL/min/1.73 m^2, then the last value on randomized treatment is considered confirmed or sustained. ESRD is defined as initiation of RRT or sustained eGFR  $<15$  mL/min/1.73 m^2 during the study (confirmed after repeat assessment of at least 14 days after initial assessment).

The following endpoint will be analyzed using a generalized mixed model repeated measure analysis using PROC GLIMMIX in SAS:

- Proportion of patients with hematuria at each visit as determined by presence of blood in urinalysis
- Proportion of patients with use of systemic immunosuppressive medication during each 12-week time bucket.

Specifically, the model will include treatment, time (ie, nominal visit in weeks), treatment by time interaction, and stratification strata factors as fixed effects, and patient as a random effect. A logit link function will be used with distribution set to binomial. An unstructured covariance matrix will be assumed; if convergence issues arise, a first order autoregressive structure will be used. Treatment effect estimates will be extracted from the model at each visit in terms of the difference between treatments in log odds, together with the associated 95% CI and 2-sided p-values. Treatment effects and CIs will be back transformed to provide results on the odds ratio scale.

At the primary analysis, analysis models without stratification by randomization strata or other simpler models may be used if sparsity of data causes model convergence issues.

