Study visits will be conducted at 2, 4, 6, and 12 weeks after randomization and at approximately 12-week intervals thereafter. Following the 110-week blinded treatment period, treatment with study medication will be discontinued for 4 weeks. At this time, the Investigator should resume standard-of-care treatment, including RAAS inhibitor treatment. Where possible, the same treatment regimen the patient was on at study entry (ie, the same ACEI and/or ARB at the same dose[s]) should be used unless, in the Investigator's opinion, an alternative treatment approach is warranted. The Investigator may make additional adjustments in anti-hypertensive medications if considered necessary to adequately control blood pressure. Patients will return to the site for the Week 114 visit after study medication has been discontinued (see [Table 1](#) and [Section 15.1](#)).

[figure not shown]
Patients who complete the double-blind period may be eligible to enroll in the open-label extension period.

Sparsentan or irbesartan concentrations (and possibly metabolites) in plasma will be evaluated. At specified visits, 1 trough sample will be obtained pre-dose in the clinic.

The primary analysis of proteinuria will be performed after the last patient randomized has undergone the Week 36 visit. Subsequently, all patients will continue to be followed on an intent-to-treat basis to Week 114 for the longer-term assessment of eGFR rate of change. Unless otherwise specified, endpoints will use the last pre-treatment value available prior to the first dose of study medication as baseline.

Flow chart and table depicting the double-blind period are provided in [Figure 1](#) and [Table 1](#).

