### **12.7.1. Analysis of the Primary Endpoint: Change from Baseline in Proteinuria at Week 36**

After approximately 280 patients have undergone the Week 36 visit, proteinuria (UP/C) data will be analyzed via a mixed-model repeated-measures analysis. Change from baseline during the double-blind period in UP/C on the log scale will be the dependent variable. Log baseline UP/C will be included as a covariate along with fixed effects for randomized treatment, time (ie, nominal visit in weeks), and randomized treatment-by-time interaction. Patient will be included as a random effect. The analysis will be stratified by the randomization strata. An unstructured covariance matrix will be assumed; if convergence issues arise, the following covariance structures will be employed in order until convergence is reached: heterogeneous Toeplitz, heterogeneous Compound Symmetry, heterogeneous first-order, auto-regressive, Toeplitz, Compound Symmetry, and first-order, auto-regressive. The treatment effect will be the contrast between sparsentan and irbesartan least squares (LS) means at Week 36. The LS means, treatment effect estimate (difference in LS means), 95% CI, and two-sided p-value will be extracted from the model. Results will be back-transformed to present treatment effects on the ratio scale.

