### **12.7.2.3. Type I Error Control for Efficacy Endpoints – Double-blind Period**

At the time of the primary analysis of change from baseline in UP/C, approximately 222 patients are projected to have eGFR data up to 58 weeks. If the analysis of UP/C at Week 36 yields a two-sided p-value <0.05, analysis of the key secondary endpoints will proceed.

[figure not shown]
For non-US countries, at the time of primary analysis of proteinuria, the key secondary endpoint of rate of eGFR rate of change over 6 to 58 weeks will be formally assessed at the 1% two-sided alpha level. Type I error control for the additional key secondary endpoints at confirmatory analysis will be governed at this time by a gate-keeper on the 6- to 58-week eGFR rate of change at the 1% level. The subsequent key secondary (confirmatory) endpoint analyses of eGFR rate of change over 6 to 110 weeks and eGFR rate of change over 110 weeks following initiation of randomized therapy will be tested sequentially and be assessed at the 4% two-sided alpha level if the 6- to 58-week eGFR rate of change analysis fails to achieve  $p < 0.01$ ; otherwise, subsequent key secondary (confirmatory) endpoint analyses will be assessed at the 5% two-sided alpha level.

For the US, at the time of primary analysis of proteinuria, the endpoint of rate of change over 58 weeks will not be formally tested. The key secondary (confirmatory) endpoint analyses of eGFR rate of change over 110 weeks following initiation of randomized therapy and eGFR rate of change over 6 to 110 weeks will be tested sequentially and assessed at the 5% two-sided alpha level.

The 2 confirmatory endpoints are intended to support regulatory submissions in the US (rate of change in eGFR over 110 weeks following initiation of randomized therapy) and non-US countries (6- to 110- week eGFR rate of change); hence, no further multiplicity adjustment is necessary. The Type I error control framework for the primary proteinuria and key secondary endpoints for US and non-US countries are displayed in [Figure 5](#). At the time of the final analysis, if all the key secondary endpoints achieve statistical significance, the other secondary endpoints will be statistically tested at the available alpha. For all other supportive efficacy endpoints, nominal p-values will be presented without Type I error control.

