## 5. PLANNED ANALYSES

### 5.1. Primary Analysis - Double-Blind Period

The primary analysis of proteinuria will be conducted on the Primary Analysis Set (PAS) after 36 weeks following randomization of approximately 280 patients to determine whether the primary efficacy endpoint, the change from baseline in UP/C, is statistically significant. As UP/C is a highly right-skewed variable, analyses will be performed on log-transformed data. The statistical evaluation of the primary efficacy endpoint will be performed using available data from all patients at the time of primary analysis, which will use a mixed model repeated measures (MMRM) analysis, at the significance level of  $\alpha = 0.05$ .

Unblinded analysis on select efficacy and safety endpoints will also be conducted.

The primary analysis will be conducted by the unblinded statistical subteam, and analysis results will not be disseminated among the Investigators and those directly involved with ongoing study conduct. Details on primary analysis procedures including formation of the unblinded subteam, interim database lock, unblinding procedures, management of unblinded analysis results, and management of documents containing unblinded analysis results will be finalized prior to primary analysis.

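### The two urine-protein responder endpoints that run up to Week 110 are analysed at the primary analysis with no allowance for incomplete follow-up, so the reported proportions would depend on accrual

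*SAP*

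**What the plan says.** SAP section 8.7.4 covers the responder endpoints. It schedules them for both analyses ("Responder endpoints will be summarized at both the primary and final analysis") and allows two outcomes only: "For these responder endpoints, patients are classified as either a responder or a non-responder". One endpoint reads "The proportion of patients achieving urinary protein excretion <0.3 g/day up to Week 110", and a second has the same form with a threshold of 1.0 g/day. Both are fitted by logistic regression with treatment, baseline urine protein excretion and the randomization strata.

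The analysis set comes from SAP section 8.7: "All other secondary and exploratory endpoints will be evaluated using the FAS". Under SAP section 6.3.1 the FAS is everyone randomized and dosed, with no minimum follow-up.

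The primary analysis is dated in three places. SAP section 5.1 puts it "after 36 weeks following randomization of approximately 280 patients". Protocol section 12.7.1 says "After approximately 280 patients have undergone the Week 36 visit". Protocol section 6.2.1 says "The primary analysis of proteinuria will be performed after the last patient randomized has undergone the Week 36 visit". Protocol section 12.7.2.3 adds that at that point "approximately 222 patients are projected to have eGFR data up to 58 weeks". Planned enrolment is about 380.

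**The concern.** A window to Week 110 can be assessed in full only for patients who could have been followed that long. At the primary analysis most could not. A patient whose urine protein has already fallen below the threshold is a responder whatever the follow-up. A patient still on treatment who has not yet got there has an open outcome, and the two-way classification has no category for that. If such patients are counted as non-responders, the proportion mixes short and long follow-up and falls below the quantity its label names.

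Elsewhere the SAP does deal with incomplete follow-up:

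- The one-year eGFR slope is limited to patients due through Week 58 (section 8.2).
- Time-to-event endpoints censor ongoing patients (section 8.7.4.1).
- Event counts carry an exposure offset (section 8.7.5).
- Hematuria is modelled by visit (section 8.7.4).

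The two urine-protein endpoints have no counterpart. The sparsity provisions in sections 8.1 and 8.7.4 concern only model convergence.

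At stake are the absolute response proportions reported beside the Week 36 proteinuria result. They would be too low as estimates of response by Week 110, and not comparable with the same-named proportions at the final analysis.

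**Working it through.** **The plan's own figure.** The only stated figure on maturity is 222 patients with eGFR data to Week 58. It cannot be reproduced, because no accrual rate is given. It is used here as an input. Uniform accrual and no loss to follow-up are assumed throughout.

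**Step 1: how many have reached Week 110?**

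*Timing 1 (280 patients at Week 36, Protocol 12.7.1 and SAP 5.1).*
- Accrual = (280 − 222)/(58 − 36) = 58/22 = 2.64 per week.
- Randomized so far = 280 + 36 × 2.64 ≈ 375, close to the planned 380.
- Followed for 110 weeks or more = 222 − 52 × 2.64 ≈ 85.
- Window still open = 1 − 85/380 ≈ 78% (77% on 375).

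*Timing 2 (last randomized patient at Week 36, Protocol 6.2.1).*
- Accrual = (380 − 222)/22 = 7.18 per week.
- Longest follow-up = 36 + 380/7.18 ≈ 89 weeks.
- Nobody has reached Week 110, so 100% of windows are open.

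**Step 2: effect on the proportion.** The documents give no response rates, so this is an illustration. Cumulative response by week t is F(t) = 1 − exp(−H (t/110)^s), with H = −ln(1 − P) and P the true proportion by Week 110. Shape s = 1 is a constant rate; s = 0.25 is strongly front-loaded. Response is detected at the urine visits in SAP Table 1 (Weeks 4, 6, 12, 24, 36 and so on). Anyone not yet a responder at the last visit reached is counted as a non-responder.

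| True P | Response pattern | Timing 1, about 375 patients | Timing 2, 380 patients |
|---|---|---|---|
| 20% | constant rate | 11.8% | 10.9% |
| 30% | constant rate | 17.9% | 16.8% |
| 20% | front-loaded | 16.5% | 17.1% |
| 30% | front-loaded | 25.0% | 25.9% |

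If only the 280 patients with Week 36 follow-up are counted under timing 1, a true 20% appears as about 15% at a constant rate. If every response occurs by Week 36, a true 20% stays at 20% in those 280 and under timing 2, and appears as about 17% across the 375 of timing 1.

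For true values from 10% to 60%, in the full set of 375 or 380, the simple proportion is about 53% to 63% of the Week 110 value at a constant rate, and about 82% to 90% when front-loaded.

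**Step 3: effect on the odds ratio.** In the same calculation, 20% against 30% has a true odds ratio of (0.30/0.70)/(0.20/0.80) = 1.71, which becomes 1.64 to 1.69. A true 2.25 (10% against 20%, or 40% against 60%) becomes 1.91 to 2.23. All movement is toward 1, and most of it is small because 1:1 randomization balances follow-up.

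**Step 4: does another reading avoid the problem?** Suppose incomplete non-responders are dropped but early responders kept. With a true 20% at a constant rate among the 280:
- Responders = 15% × 280 = 42.
- Fully followed non-responders = 85 × 80% = 68.
- Proportion = 42/(42 + 68) = 38%.

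The same data give about 15% or 38%, depending on a choice the SAP leaves open.

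**The case against.** The strongest reply is that the SAP nowhere says unreached visits count as non-response. Its conventions in sections 6.1 and 6.2 base percentages on non-missing data, so by default a patient with no post-baseline urine would leave the denominator. That stands, and it means the scoring rule is inferred. But the conventions do not settle the much larger group with some visits and no response yet. Using the visits available for them gives the understated figure.

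Other parts of the reply also stand:

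- **Status.** Both endpoints are exploratory and outside the testing order in SAP section 8.4.3, with nominal p-values under Protocol section 12.7.2.3. Protocol section 4.7 ties the application for approval to the Week 36 change in proteinuria, not to these proportions.
- **Timing of response.** The early proteinuria effects described in Protocol sections 4.2 and 4.3 (6 weeks with a related drug, 8 weeks with sparsentan) make the front-loaded end of the range plausible.
- **Existing fixed-time definition.** SAP section 8.3 defines response below 0.3 g/day at Weeks 36, 58 and 110, but only to form subgroups, and not for 1.0 g/day.
- **Labelling.** Read as achieved by the data cut-off, the simple proportion is a valid description.

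A reader might infer that the kidney composite (40% eGFR reduction, ESRD or death), listed in the same section, has the same fault. The documents do not support that. A responder there has had an unfavourable event, so an ongoing patient counts as event-free rather than as a failure. Its entry carries no Week 110 window, and SAP section 8.7.4.1 already plans a censored, stratified Cox analysis of it at both analyses.

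**Conclusion.** The point holds for the two urine-protein endpoints at the primary analysis only. The plan reports proportions with a Week 110 window when roughly 78% to 100% of patients have not reached Week 110, and gives no method or denominator that accounts for this. On the natural reading, the absolute proportions depend on accrual and understate the Week 110 value: a true 20% appears as about 11% to 15% at a constant response rate, or about 17% to 20% if responses come early. These sizes rest on assumed uniform accrual, no loss to follow-up and assumed response patterns.

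Two stronger readings are tempting and not supported. One is that the treatment comparison is seriously biased; the odds ratio is only mildly attenuated. The other is that a confirmatory conclusion is at risk; no alpha is attached to these endpoints. The final analysis takes place after every patient has reached Week 114 or terminated early (SAP section 5.2), so the problem does not arise there. This is a cheap improvement to reporting, not an error in the primary inference.

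**What to change.** In SAP section 8.7.4, for the primary analysis, replace the plain logistic regression of the two urine-protein endpoints with one of the following:

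1. Time to first value below 0.3 g/day and time to first value below 1.0 g/day, using Kaplan-Meier estimates and a Cox model stratified by the randomization strata as in section 8.7.4.1. Ongoing patients are censored at their last on-treatment 24-hour urine.
2. Response by Week 36 among patients randomized at least 36 weeks before the data cut.

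Keep the Week 110 proportions and their logistic regression for the final analysis. Label any simple proportion shown at the primary analysis as achieved by data cut-off, and state its denominator. The composite needs no change on this account.

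The cost is a few lines of SAP text and one extra table, with no new data. The second option leaves out patients not yet due for Week 36.
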